#### **17.4. Interim analyses**

Interim analyses will be performed for safety, and the DSMC will have the ability to halt the trial at any time. Full DSMP reports will be produced after 10, 20, 30, and 45 patients are randomized and at least semi-annually based on the date of enrollment of the first patient. Toxicity monitoring will be performed using a frequentist approach and targeting an excess rate of toxic death of no more than 5%. Toxicity will be monitored for each arm at the same 4 time points. Sequential boundaries will be calculated using the Pocock method. If the number of toxicities differs in any one study by 3, 4, 5, or 7 patients corresponding to the assessments above, enrollment will be halted and toxicities will be further evaluated to assess if it is appropriate to terminate the study. This stopping boundary yields a probability of early stopping of at most 0.05 when the dose-limiting toxicity is equal to 0.05. Toxic death will be adjudicated by the DSMC. There are no plans for fertility monitoring because of the relatively small size of the proposed trial, non-invasiveness of the samples collected, and the potential for longitudinal study results to add significant mechanistic understanding to MDRO colonization in the ICU.

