#### Retention

Potential loss of patients after randomization will be from death/discharge prior to ICU Day 3, or withdrawal of consent (e.g., after initial surrogate consent). In our ongoing ICU cohort studies, there has been 11.3% mortality within 3 days and a 0% Day 3 discharge rate. Additional patients will be enrolled for patients who do not complete the Day 3 assessment due to death or discharge. Thus, we expect to enroll 102 patients to obtain 90 who are able to donate a Day 3 sample and therefore can included in the intent-to-treat analysis.

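### Section 17.4 gives numeric toxicity limits only up to 45 patients randomized, although about 102 are expected, and the unit that the limits count is not settled

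*Combined protocol and SAP*

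**What the plan says.** Section 17.4 (Interim analyses) sets the schedule: "Full DSMP reports will be produced after 10, 20, 30, and 45 patients are randomized and at least semi-annually". It then says "Toxicity will be monitored for each arm at the same 4 time points", and "Sequential boundaries will be calculated using the Pocock method". The trigger reads "If the number of toxicities differs in any one study by 3, 4, 5, or 7 patients corresponding to the assessments above", after which enrollment is halted and the toxicities are evaluated. The claimed property is: "This stopping boundary yields a probability of early stopping of at most 0.05 when the dose-limiting toxicity is equal to 0.05". No limit is given for any look after 45.

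Under Retention in Section 12, "we expect to enroll 102 patients to obtain 90" who can give a Day 3 sample. Section 16 continues the study until 90 patients have completed the Day 3 assessment. Allocation is 1:1:1 (Sections 9 and 12.1).

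**The concern.** A sequential boundary protects patients only while it has looks left. Here the last look falls before the midpoint of expected enrollment, and both inulin doses open together with no escalation step. A toxicity rate that needs more than 45 patients to show itself is never compared with a limit. The early-stopping sentence then describes the first 45 patients and not the trial.

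A second weakness decides how much the first one matters. Section 17.4 monitors by arm, triggers on a number that differs, and states its error rate for a single 5% rate. These are three different units. The limits 3, 4, 5 and 7 mean very different things under each, so neither the present rule nor an extension of it can be evaluated until the unit is fixed.

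**Working it through.** **Inputs.** Looks at 10, 20, 30 and 45 randomized, limits 3, 4, 5 and 7, null rate 0.05 and stated stopping probability of at most 0.05 (all Section 17.4); 11.3% loss by Day 3 and 102 expected (Section 12, Retention); 1:1:1 allocation (Section 12.1). The 15% alternative is this review's assumption; the plan names none.

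**1. Enrollment.** 90 / (1 − 0.113) = 101.5, so 102 reproduces.

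**2. Coverage.** (102 − 45) / 102 = 57/102 = 55.9%. Against 90: (90 − 45) / 90 = 50%. At 1:1:1, about 57 × 2/3 = 38 of the 57 receive inulin.

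**3. The plan's own error figure.** Method: exact binomial recursion. At each look, add the new patients' binomial count to the running total, remove the probability at or above the limit, and carry the rest forward. With one cumulative count at 10/20/30/45 and a rate of 5%, the first-crossing probabilities are 0.0115 + 0.0107 + 0.0072 + 0.0021 = 0.0315. This agrees with the stated ceiling of 0.05. If a limit must be exceeded rather than reached, the figure is 0.006.

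**4. Detection on that pooled reading.** The crossing probability is 0.263 at 10%, 0.624 at 15% and 0.871 at 20%. The miss at 15% is 1 − 0.624 = 37.6%. The 15% is then a rate over all three arms, placebo included. If inulin is at 15% and placebo at 5%, the pooled rate is (15 + 15 + 5)/3 = 11.7%; detection is 38% and the miss 62%.

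**5. The other readings, at 15%.**

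| Reading of 3/4/5/7 | Miss |
|---|---|
| One count over all arms at 10/20/30/45 in total | 37.6% |
| Each arm counted at 10/20/30/45 in total (about 3/7/10/15 per arm) | 98% |
| Looks are per-arm numbers (an arm of about 34 never reaches 45) | 47.5% |
| Inulin minus placebo, 15% against 5%, looks at 10 to 45 per arm | about 62% |
| Inulin minus placebo, 15% against 5%, about 3 to 15 per arm | about 99% |

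The third row has no coverage gap of the size in step 2, because an arm reaches 30 when about 90 are enrolled in total.

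**6. Does an extension fit within 0.05?** Pooled-count reading only, with looks added at 60, 75 and 90 and illustrative limits 8, 9 and 10:

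| True rate | Four looks | Seven looks |
|---|---|---|
| 5% | 3.1% | 4.4% |
| 10% | 26% | 50% |
| 15% | 62% | 91% |
| 20% | 87% | 99% |

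**7. Why the limits must be recalculated on the chosen unit.** Counting per arm at total-randomized looks, the same added limits 8/9/10 move detection at 15% only from 1.9% to 2.9%. Limits built for that unit behave differently. For illustration, 2/3/3/4/4/5/5 at about 3/7/10/15/20/25/30 per arm gives 53% detection at 15%, against 25% if it stops at the fourth look, with a 3.4% false-stop probability per arm. Over three independent arms that is 1 − (1 − 0.034)³ = 9.8%, so the plan must also say whether 0.05 is per arm or trial-wide.

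**The case against.** The strongest reply is that no numeric limit does not mean no monitoring. Full reports continue at least semi-annually, and the committee may halt at any time (Section 17.4). Serious unanticipated problems are reported within 24 hours (Section 15.2), and the Research Monitor may stop the protocol (Section 15.2.1). Dosing ends for a patient with a related adverse event (Section 12.3). All of this stands, and a reader should not infer that the later patients are unmonitored. None of it, however, supplies a trial-level trigger or an error property.

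A reader might also infer, as a fact about the plan, that a 15% rate is missed 38% of the time. The documents do not support that. The figure needs a count pooled over all arms, whereas Section 17.4 says toxicity is monitored by arm, and 15% is not the plan's number. The plan promises only a false-stop ceiling, so no stated detection target is breached.

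If the looks were per-arm numbers, the rule would run to about 90 patients in total and the coverage gap would largely close. The text counts patients randomized without any per-arm qualifier, so this is the less natural reading, but the wording should exclude it.

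Early-weighted looks are also a defensible preference in a 90-patient phase 2 trial of a fiber for which the protocol cites no serious adverse events. On the pooled reading at 15%, extending the looks lowers expected enrollment only from about 53 to about 44. That tempers the gain but gives no reason for ending at 45, and Section 17.4 offers none. Finally, the DSMP was not available and may add detail. It cannot be presumed to override a section that itself fixes four time points.

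**Conclusion.** The point holds as a coverage gap joined to an undefined unit. With looks indexed to total patients randomized, about 57 of 102 expected patients (56%; half of 90) are randomized after the last numeric limit. Detection by the four looks cannot be given as one number: at an assumed 15% rate the miss is about 38% on the pooled-count reading and about 98% when each arm is counted at about 3/7/10/15 patients. The stated ceiling of 0.05 is consistent with the pooled count (0.031) and leaves room for later looks on that reading. The coverage figure rests on the expected enrollment of 102 and on the plain reading of the look schedule. The detection figures rest on the assumed rate, on a limit being reached rather than exceeded, and on the unit. The change should be made; confidence is medium because of the open unit and the unseen DSMP.

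**What to change.** In Section 17.4, and in the DSMP to match:

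1. State one unit for the limits (each arm, pooled, or a difference between arms) and whether the looks count total or per-arm patients. Reconcile the monitoring, trigger and error-rate sentences to it.
2. Continue the boundary looks to the end of enrollment, for example at 60, 75 and 90 randomized.
3. Recalculate all limits on that unit by the stated Pocock approach, so that the overall early-stopping probability at a 5% rate stays at or below 0.05. Say whether this applies per arm or trial-wide, and restate the property for the full trial.
4. If the limits are meant to end at 45, say so and give the reason.

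All limits shown here beyond the plan's own four are illustrations; the sponsor and the DSMC must choose the actual ones. The cost is a wording change and about three more reports from a data center that already reports at least semi-annually. The downside is a somewhat higher chance of a false pause: on the pooled illustration, 4.4% instead of 3.1% at a 5% rate.

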## 9. Intervention

Block randomization (blocks of six) will be performed with 1:1:1 random computer allocation of subjects into the three study arms. In the two inulin arms, chicory root-derived inulin (Cargill Inc., Wayzata, MN) will be diluted in 250 ml of sterile water and given at 8 or 16 g twice daily (**Figure 4**). The placebo arm will receive the same volume of sterile water twice daily, with the intervention given for 7 days or until death or hospital discharge. Prior studies suggest that these doses are likely to be safe and sufficient to confer benefit, even in the setting of critical illness. Subjects, investigators, and the treating ICU team will be blinded to the intervention arm, with blinding managed by the CUMC Research Pharmacy which will provide labeled, de-identified, semi-opaque fluid bags containing inulin/placebo in accordance with the U.S. Code of Federal Regulations governing labelling of new investigational drugs (21CFR 312.6). The intervention will be taken orally or given with enteric feeding by nursing staff overseen by the study team, with the first dose administered within 6 hours of ICU admission. The time course for the intervention and remaining study assessments is shown below in **Table 3**.

**Figure 4.** Chemical structure of inulin. Inulin is a naturally occurring polysaccharide derived from chicory root, agave, garlic, and other vegetable sources; it is a long chain carbohydrate of fructose polymers with  $\beta(1,2)$  glycosidic linkages which are indigestible by human enzymes but fermented by colonic anaerobic bacteria into short-chain fatty acids (chemical formula:  $C_{6n}H_{10n+2}O_{5n+1}$ ).

**Table 3.** Time course of intervention and main assessments during the study.

Type of Assessment	Inulin----->			Monitoring----->			
	Day 0	Day 3	Day 7	Day 14	Day 30	3 months	6 months
Rectal swab	X	X	X	X	X		
Whole stool	X	X	X	X	X		
Clinical data	X	X	X	X	X	X	X
Telephone follow-up						X	X

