### **15.2. Adjudicating and reporting adverse events as unanticipated problems**

Unanticipated problems (UPs) will be any unforeseen medical event thought likely related to the study intervention. Such events will be monitored for in real time. UPs that do not meet criteria for seriousness (same as SAE criteria) will be reported to the DSMO and IRB at pre-specified intervals. UPs that meet criteria for seriousness will be reported within 24 hours from our notification of the event. This reporting will include:

- Contact of the DSMO;
- Contact of the Columbia IRB;
- Fax or email scan containing when the event occurred, the name of the reporter, callback information, the protocol number, and a description of the event;
- Availability of the PI to provide follow-up information regarding the event.

The proposed research is pending review by the Columbia University IRB (IRB #AAAS2576) and will be reviewed by the U.S. Army Medical Research and Materiel Command (USAMRMC) Office of Research Protections (ORP), Human Research Protection Office (HRPO) prior to implementation. Prior to initiation of research, the study will be registered on [clinicaltrials.gov](http://clinicaltrials.gov).

Safety and adverse effects will be overseen by the PI in conjunction with the Data and Safety Monitoring Officer (DSMO). **[name]**, the Director of the Medical Intensive Care Units at our institution will serve as the trial DSMO and will convene an appropriate Data and Safety Monitoring Committee (DSMC) to oversee interim study results. The primary responsibility of the DSMC will be to review interim data in terms of safety and make recommendations whether the study should be changed, halted, or terminated. Full details of the DSMC procedures and processes as well as additional details regarding AE and SAE reporting are in the DSMP.

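### The toxicity boundary 3/4/5/7 fits one group of 10/20/30/45 patients, but section 17.4 monitors each arm, which has only about 3/7/10/15 patients at those looks

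*Combined protocol and SAP*

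**What the plan says.** All the elements are in section 17.4 of the combined protocol and SAP.

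- Timing: "Full DSMP reports will be produced after 10, 20, 30, and 45 patients are randomized".
- Unit: "Toxicity will be monitored for each arm at the same 4 time points".
- Method: "Sequential boundaries will be calculated using the Pocock method".
- Trigger: "If the number of toxicities differs in any one study by 3, 4, 5, or 7 patients corresponding to the assessments above". Enrolment is then halted while the toxicities are evaluated.
- Stated property: "This stopping boundary yields a probability of early stopping of at most 0.05 when the dose-limiting toxicity is equal to 0.05".

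Section 9 gives the allocation: "Block randomization (blocks of six) will be performed with 1:1:1 random computer allocation of subjects into the three study arms". Section 11.1 targets 30 patients per arm who complete Day 3, and the Retention paragraph of section 12 expects 102 enrolled to obtain those 90.

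**The concern.** The look times are trial totals. They cannot be arm counts, because no arm reaches 45: the target is 30 completers per arm, and 102/3 = 34 enrolled. An arm therefore has about a third of the patients that the look times suggest. Limits that are reasonable for 10, 20, 30 and 45 patients become very high for 3, 7, 10 and 15.

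This is the only numerical safety trigger in the plan. If it is too insensitive for the unit it monitors, harm confined to one inulin dose would rarely cross it, and the committee could take a boundary not crossed as more reassurance than it gives.

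The wording also leaves the rule open to different programming. There is only one study, so a difference in any one study names no comparison. The event is variously a toxic death, a toxicity and a dose-limiting toxicity. The 5% appears once as an excess rate and once as a plain rate.

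**Working it through.** **Assumptions.** Each counted toxicity is one adjudicated event, and 5% is the absolute rate in an arm. Enrolment halts when the count reaches the limit.

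**1. Reproducing the printed limits.** Under a Pocock rule every look uses the same nominal level. For four looks at 10, 20, 30 and 45 and an overall 0.05, that level is 0.0188 one-sided or 0.0178 two-sided (normal approximation, simulated). The limit at each look is the smallest r with P(X ≥ r) at or below this level, where X ~ Binomial(n, 0.05).

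| n | Printed limit r | P(X ≥ r) | P(X ≥ r − 1) |
|---|---|---|---|
| 10 | 3 | 0.0115 | 0.086 |
| 20 | 4 | 0.0159 | 0.075 |
| 30 | 5 | 0.0156 | 0.061 |
| 45 | 7 | 0.0066 | 0.0239 |

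Any constant level from 0.0159 to just under 0.0239 gives exactly 3/4/5/7. The exact sequential binomial probability of crossing at any look is 0.0315 at a 5% rate, which agrees with the stated maximum of 0.05. The limits therefore fit one group of 10/20/30/45.

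**2. Arm sizes at the looks.** Each full block of six puts two patients in each arm, and a partial block adds 0 to 2.

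- 10 = 1 block + 4 patients: 2–4 per arm
- 20 = 3 blocks + 2: 6–8 per arm
- 30 = 5 blocks: 10 per arm
- 45 = 7 blocks + 3: 14–16 per arm

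**3. The same construction at arm sizes.** At 3/7/10/15 the tails for limits 2/3/3/4 are 0.0073, 0.0038, 0.0115 and 0.0055. One count lower they are 0.143, 0.044, 0.086 and 0.036. So every level in the range from step 1 gives 2/3/3/4. The same holds at both block extremes, 2/6/10/14 and 4/8/10/16, so the mismatch does not depend on the arm split.

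**4. Probability that one arm triggers** (exact sequential binomial; block extremes in brackets):

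| True rate in the arm | Printed 3/4/5/7 at 3/7/10/15 | Same construction, 2/3/3/4 |
|---|---|---|
| 5% | 0.03% (0.01–0.08%) | 1.8% (1.4–2.4%) |
| 20% | 5.6% (4.2–8.2%) | 43% (39–48%) |
| 30% | 22% (18–29%) | 76% (71–80%) |

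For an arm of 3/7/10/15, the printed limits require 3 of 3, 4 of 7, 5 of 10 or 7 of 15 patients. An arm with only two patients at the first look cannot trigger there at all.

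**5. Other readings of the rule** (simulated permuted blocks of six; placebo and low dose at 5%, high dose as shown):

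| Reading, printed limits | High dose 20% | High dose 30% |
|---|---|---|
| High-dose count minus placebo count | 4.3% | 17% |
| All three arms pooled | 25% | 51% |

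The difference reading is no more sensitive than the per-arm count; with 2/3/3/4 it would give about one third at 20%. The pooled reading has the properties of step 1 (about 3.1% when every arm is at 5%), but it contradicts the per-arm statement and dilutes harm confined to one arm. For comparison, one group of 10/20/30/45 that is entirely at 20% triggers with probability 87%.

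**The case against.** The strongest defence is that no printed figure is false. The plan claims only that early stopping has probability at most 0.05 at a 5% rate, and that holds pooled (0.0315), per arm (0.0003) and as a between-arm difference (about 0.0004). It promises no power to detect toxicity. This stands, but the property is met per arm only because the rule is almost inert, and the limits were not derived for the arm sizes.

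The trigger sentence does not itself say that the limits apply to a count in an arm, and that they were built for one pooled group is an inference. This also stands. However, the printed limits are insensitive under both arm-level readings, and the pooled reading contradicts the preceding statement of the unit.

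Other safeguards exist: "the DSMC will have the ability to halt the trial at any time", toxic deaths are adjudicated by the committee, and under section 15.2 "UPs that meet criteria for seriousness will be reported within 24 hours from our notification of the event". The boundary triggers a pause for review, not termination. These points limit the consequence, and any false reassurance of the committee is a risk rather than a certainty.

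Section 15.2 refers to the DSMP for full committee procedures. That plan is not available here and may define the unit, but section 17.4 would still need correction.

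Finally, the limits 2/3/3/4 slightly exceed 0.05 across three arms. Limits that stay below it trial-wide, such as 2/3/4/4 or 3/3/4/4, give 39% and 37% at a 20% rate. The recoverable gain is then a little smaller but still large beside 5.6%.

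**Conclusion.** The concern holds and should be corrected before the rule is relied on. The limits 3/4/5/7 match a single group of 10/20/30/45 and do not match the arms that section 17.4 says are monitored. At four times the reference rate (20% against 5%), the per-arm trigger probability is about 6%, against about 43% for the same construction at the true arm sizes. The false-stop limit is not breached; what is lost is sensitivity.

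The 6% and 43% rest on an absolute count per arm, a 5% absolute reference rate and arm sizes near 3/7/10/15. The direction is the same over all block splits and under the inulin-minus-placebo reading. The mismatch itself is certain from the text. How much it matters in practice depends on the committee's other powers and on the DSMP.

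**What to change.** Reconcile the monitored unit with the limits in section 17.4 and in the DSMP, in one of two ways:

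- **Monitoring by arm:** recompute the limits at the actual number of patients in each arm at each look. The 2/3/3/4 above is an illustration, not a recommendation.
- **Pooled monitoring:** remove the per-arm statement and acknowledge that harm in one arm is diluted.

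In either case:

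- Name the quantity compared: the count in an arm, inulin arm minus placebo, or the pooled count.
- State whether the 0.05 limit applies per arm or across the trial.
- Use one event definition throughout, and say whether 5% is an absolute or an excess rate.
- Report trigger probabilities at harmful rates as well as at 5%.

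The choice of boundary, and whether to add boundary looks after 45 patients, is for the sponsor and the monitoring committee.

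The work is recalculation and rewording. The price of a more sensitive per-arm rule is more enrolment pauses. With 2/3/3/4 and all three arms at 5%, the chance of any pause rises from about 0.1% to 1 − (1 − 0.0184)³ = 5.4% (6.0% with simulated blocks of six). With all three arms at 10%, it rises from 1.4% to about 29%. Section 12 reports 11.3% three-day mortality in the investigators' cohorts, so careful attribution of deaths will matter to how often such a rule fires.

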#### **18. Publication policy**

Study results will be disseminated as widely as possible by publication and presentation. The PI is ultimately responsible for publications arising from the study. Funding sources will be recognized.

## Appendix B: Abbreviations and terms

ADLs	activities of daily living
AE	adverse event
ANOVA	analysis of variance
APACHE	acute physiology and chronic health evaluation
ASPEN	American Society for Parenteral and Enteral Nutrition
BMI	body mass index
CDC	Centers for Disease Control and Prevention
CDI	Clostridium difficile infection
CFU	colony-forming units
CLP	cecal ligation and puncture
CRF	case report form
CUMC	Columbia University Medical Center
DNI	Do not intubate
DNR	Do not resuscitate
DCC	Data Coordinating Center
DSMC	data and safety monitoring committee
DSMO	data and safety monitoring officer
ECMO	extra-corporeal membrane oxygen
EDTA	ethylenediaminetetraacetic acid
EMR	electronic medical record
EQ-5D-5L	EuroQol 5-dimension 5-level questionnaire
ER	emergency room
ESBL	extended-spectrum beta-lactamase
FDA	Food and Drug Administration
GCS	Glasgow coma scale
GI	gastrointestinal
GMP	good manufacturing practices
GRAS	generally recognized as safe
HRPO	human research protection office
IABP	intra-atrial balloon pump
ICD	International classification of diseases
ICU	intensive care unit
IND	investigational new drug
IQR	interquartile range
IRB	institutional review board
KPC	Klebsiella pneumonia carbapenemase
LAR	legally authorized representative
LDA	least discriminant analysis
LEfSe	linear discriminant analysis effect size

LPS	lipo-polysaccharide
MDR	multidrug resistant
MDRO	multidrug resistant organism
MRSA	methicillin-resistant Staphylococcus aureus
NHSN	National Health and Safety Network
OR	operating room
ORP	Office of Research Protections
OTU	operational taxonomic unit
PCR	polymerase chain reaction
PI	primary investigator
PICRUST	phylogenetic investigation of communities by reconstruction of unobserved states
PPIs	proton pump inhibitors
PRMRP	peer-reviewed military research projects
QIIME	Quantitative Insights Into Microbial Ecology
qPCR	quantitative polymerase chain reaction
REDCap	Research Electronic Data Capture
rRNA	ribosomal ribonucleic acid
RT-PCR	real-time polymerase chain reaction
SAE	serious adverse event
SCFA	short-chain fatty acids
SD	standard deviation
SAPS3	simplified acute physiology score-3
SIRS	systemic inflammatory response syndrome
SOFA	sequential organ failure assessment
TNF	tumor necrosis factor
USAMRMC	U.S. Army Medical Research and Materiel Command
VRE	vancomycin-resistant Enterococcus
WGS	whole genome sequencing
